## **5.5 Baseline assessment (T1)**

The following assessments will be completed prior to randomization, preferably within one week of screening assessment (T0). Subjects have the option of completing the screening and baseline assessments on the same day. Due to the ongoing COVID-19 pandemic, some of the baseline measures may be completed either in person, via phone or Zoom.

***Demographics, clinical and treatment/cancer characteristics will be collected.***

### **Socio-Demographics and Clinical Characteristics**

Patient's age, race, ethnicity, gender, highest level of education achieved, employment status, and marital status, will be captured from the subjects. The socio-demographics and clinical characteristics will be collected at baseline.

### **Clinical Record Form**

Type of colorectal neoplasm, prior malignancy, and treatment regimen will be abstracted from the medical records. This information will be collected at baseline only.

### **Outcomes of Interest (baseline and post-intervention unless otherwise specified)**

#### **Geriatric Assessment Measures for DAFI calculation**

Items from the Geriatric Assessment will be used to calculate the deficit accumulation frailty index (DAFI) to assess subjects' frailty status at the baseline assessment (T1) and at the post-intervention assessment (T2).

*Activities of daily living (ADL):* ADLs are measures of self-care. ADL independence will be assessed using the Katz Index of Independence in Activities of Daily Living, commonly referred to as the Katz ADL. The Katz ADL is the most appropriate instrument to assess functional status as a measurement of the client's

ability to perform activities of daily living independently. Clinicians typically use the tool to detect problems in performing activities of daily living and to plan care accordingly. The index ranks adequacy of performance in the six functions of bathing, dressing, toileting, transferring, continence, and feeding. Clients are scored yes/no for independence in each of the six functions. A score of 6 indicates full function, 4 indicates moderate impairment, and 2 or less indicates severe functional impairment.

*Instrumental Activities of Daily Living (IADL):* Self-reported functional status will be assessed using the IADL subscale of the Multidimensional Functional Assessment Questionnaire: Older American Resources and Services (OARS). The IADL subscale consists of seven questions rated on a three-point Likert scale. It measures the degree to which an activity can be performed independently.

*Fall History:* A self-reported history of falls in the past three months will be recorded. A history of a recent fall has been demonstrated to be independently predictive of increased risk for chemotherapy toxicity in older patients with cancer.

*Timed Up and Go:* The Timed Up & Go is a performance based test of functional status, measuring how many seconds it takes to stand up from a standard arm-chair, walk 3 meters (10 feet), turn, walk back to the chair, and sit down again.

*Nutritional Status and Mini Nutrition Assessment (MNA):* Screening for nutritional deficit will be performed with body mass index (BMI) evaluation and self-reported weight loss. Further nutritional evaluation will be performed with the Mini-Nutritional Assessment (MNA), a well validated screening measure for nutritional deficiency which has shown to be prognostic of survival in older patients with cancer. Weight will be assessed at the screening assessment (T0) and at the post-intervention assessment (T2). Height will be assessed at baseline.

*Cognition:* Montreal Cognitive Assessment (MoCA): A 30-point cognitive screen test with excellent sensitivity for individuals with mild dementia and mild cognitive impairment. It can also be used to trend changes in cognitive status over time.

*Comorbidity:* OARS Physical Health Section: Patients self-report their coexisting medical conditions and also rate the degree to which their illness causes impairment in daily activities. The OARS Physical Health Section has been shown to correlate significantly with health professional ratings of comorbidity as well.

*OARS Medical Social Support and Social Activities:* A 13-question survey asking patients to identify the number of support persons involved in their medical care as well as the degree to which they felt supported in a variety of situations. A follow-up question will be used to assess how much a patient's physical or emotional health interfered with social activities.

*Medications (baseline only):* We will record all prescription and non-prescription medications, dosage and frequencies from the medical records. We will also do medication reconciliation with the oncology team to determine the accuracy of all possible medications that the subject is taking. Polypharmacy is defined as the use of 5 or more medications.

*Generalized Anxiety Disorder 7 (GAD-7):* The GAD-7 is a self-administered patient questionnaire used as a screening tool and severity measure for generalized anxiety disorder. The GAD7 score is calculated by assigning scores of 0, 1, 2, and 3, to the response categories of "hardly ever," "several days," "more than half the days," and "nearly every day," respectively, and adding together the scores for the seven questions. Scores of 5, 10, and 15 are taken as the cut off points for mild, moderate, and severe anxiety, respectively. When used as a screening tool, further evaluation is recommended when the score is 10 or greater. Using the threshold score of 10, the

GAD-7 has a sensitivity of 89% and a specificity of 82% for generalized anxiety disorder. It is moderately good at screening three other common anxiety disorders – panic disorder (sensitivity 74%, specificity 81%), social anxiety disorder (sensitivity 72%, specificity 80%), and post-traumatic stress disorder (sensitivity 66%, specificity 81%).

*Geriatric Depression Scale (GDS):* Patients will be screened with the Geriatric Depression Scale (GDS). The GDS contains questions that are intended to screen elderly patients for depression, while parsing out complaints related to advanced age.

#### Other Measures for DAFI calculation

*Physician rated Karnofsky Performance Status (KPS):* The KPS is an index that allows patients with cancer to be classified according to the presence of any functional impairments (e.g. inability to work and care for personal needs). KPS score ranges from 0-100. Low KPS scores are associated with decreased survival in patients with cancer.

*Patient rated KPS:* The patient rated KPS is a patient reported outcome of the presence of any functional impairments.

*Complete Metabolic Panel (CMP):* Study personnel will obtain lab results from the CMP from electronic medical records with dates that are closest to assessment date for baseline assessment (T1) and post-intervention assessment (T2).

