## **5.3 Data collection tables**

The following table summarizes study activities based on the 12-week intervention that all subjects will complete regardless of randomization assignment (EGCG or usual care).

Assessment	Study Goal	Completed by	Screening	Baseline (week 0)	Post-Intervention (week 13)
			T0	T1	T2
Written Informed Consent	N/A	Subject	•		
Demographics	Eligibility	Subject	•		
Eligibility Checklist	Eligibility	Research Assistant	•		
Clinical Record Form	Eligibility A2/EA1	Research Assistant	•		

Fried's Frailty Score (FFS)	Eligibility/ A2/EA1	Research Assistant	●		●
GODIN Leisure-Time Exercise Questionnaire	Eligibility	Research Assistant	●		●
Instrumental Activities of Daily Living	GA/A2/EA1	Subject		●	●
Activities of Daily Living	GA/A2/EA1	Subject		●	●
Patient Rated Karnofsky Performance Status (Patient KPS)	GA/A2/EA1	Subject		●	●
Fall History	GA/A2/EA1	Subject		●	●
OARS Comorbidity	GA/A2/EA1	Subject		●	●
Social Activities	GA/A2/EA1	Subject		●	●
OARS Medical Social Support	GA/A2/EA1	Subject		●	●
Geriatric Depression Scale (GDS)	GA/A2/EA1	Subject		●	●
Generalized Anxiety Disorder-7 (GAD7)	GA/A2/EA1	Subject		●	●
Functional Assessment of Cancer Therapy: General (FACT-G)	EA2	Subject (diagnosed with any cancer except colorectal)		●	●
Functional Assessment of Cancer Therapy: Colorectal Cancer (FACT-C)	EA2	Subject (diagnosed with colorectal cancer)		●	●
MD Anderson Symptom Inventory (MDASI)	EA2	Subject		●	●
Mini Nutritional Assessment (MNA)	GA/A2/EA1	Research Assistant		●	●
Physician Rated Karnofsky Performance Status (KPS)	GA/A2/EA1	Research Assistant		●	●
Labs	GA/A2/A3/EA1/EA3	Chart Review		●	●
Blood Requisition Form	A3 & EA3	Phlebotomist		●	●
Montreal Cognitive Assessment (MoCA)	GA/A2/EA1	Research Assistant		●	●

Short Physical Performance Battery (SPPB)	EA2	Research Assistant		•	•
Timed up and Go	EA2	Research Assistant		•	•
Yale Physical Activity Survey for Older Adults	EA2	Research Assistant		•	•
Qualitative Interview (Audio Recorded)	EA4	Research Assistant			•
Pill Count Form (Excel)	A1	Research Assistant			•
Weekly Phone Call Log (Excel)	A1	Research Assistant		•	•
Study Feedback Form	A1	Subject			•

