**Table 4: Measures Needed to Calculate the Deficit Accumulation Frailty Index (DAFI)**

Measure	Item
Demographics	Marital Status
	Telephone
	Travel
	Shopping
	Prepare Meals
	Housework
	Take Medicines
	Handle Money
	Bathing/showering
	Dressing
IADL Instrumental Activities of Daily Living (IADL)	Eating
	Getting out of bed or chairs
	walking
	Using the toilet
Activities of Daily Living (ADL)	Patient Rated KPS
	Number of Falls
	Number of regular medications taken daily
	Other cancer or leukemia
	Arthritis
	Glaucoma
	Emphysema
OARS Comorbidity	High blood pressure

	Heart disease
	Circulation trouble
	Diabetes
	Stomach/Gastrointestinal
	Osteoporosis
	Liver/kidney
	Stroke
	Depression
	Eyesight
	Hearing
Mini Nutritional Assessment (MNA)	Weight loss
Geriatric Depression Scale (GDS)	Depression
Generalized Anxiety Disorder - 7 (GAD7)	Anxiety
	Social activity
Social activities	Change of social activity in the last 6 months
	Comparison of social activity to others their age
	Confined to bed
OARS Medical Social Support	Take to MD
	Prepare Meals
	Daily chores
Physician Rated Karnofsky Performance Status	KPS
Timed-up-and-go (TUG)	Time to complete measure
Montreal Cognitive Assessment (MoCA)	Cognition
Mini Nutritional Assessment (MNA)	Body Mass Index
	Creatinine clearance
Complete Metabolic Panel	Hemoglobin
	Albumin
	Liver Function test

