4. Two PAXgene® tubes (2.5 mL each, 5 mL total). These will be used to assess gene expression (i.e., mRNA). These will be rocked 10 times and allowed to sit at room temp for 2-24 hours. Then they will be frozen at -20°C and moved to -80°C for long-term storage.
5. If we need to draw blood for a complete blood count (see below), we will draw one additional purple-top EDTA tube with 5 mL of blood.

If possible, we will obtain a complete blood count from a medical blood draw if the medical blood draw is conducted within the assessment week for T1 or T2. If there is no medical blood draw conducted within the appropriate assessment window for T1 or T2 then we will draw an additional 5 mL of blood (50 mL total) into a purple-

top EDTA tube for a complete blood count with differential analysis for our research purposes.

Inflammation will be assessed using the latest available technology (e.g., in vitro enzyme-linked immunosorbent assay; ELISA). These assays will assess the concentration of inflammatory cytokines and receptors associated with frailty including TNF- $\alpha$ , TNFRI, TNFRII, CRP, IL-1 $\beta$ , and IL-8. Additional blood biomarkers of interest already available in the medical record will be obtained as well. All human biological materials will be disposed of in adherence with the University of Rochester Office of Environmental Safety Biosafety Level II requirements. All laboratories used in the current study have received appropriate biosafety certifications by the University of Rochester Institutional Biosafety Committee and undergo routine inspections. All samples will be de-identified before being stored.

The serum concentration of EGCG at the post-intervention time-point (T2) will be assessed using the latest available technology (e.g. ultra-performance liquid chromatography-tandem mass spectrometry (UPLC-MS/MS)) available by the URMC mass spectrometry resource lab.

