## **5.9 Intervention contact and tracking**

The study coordinator will make every effort to contact each subject 1 time per week via phone calls, and/or emails, (based on each subject's preference) to encourage intervention adherence to the study drug. During this weekly contact the study coordinator will also ask about any safety concerns including: symptoms, signs, illnesses, or experiences, that develop or worsen during the study. These concerns will be graded (according to the CTCAE v5.0 see section 7), recorded, reviewed with the treating oncologist as well as the medical monitor, and reported (if necessary) according to the outline in section 7. If medical information needs to be further discussed, we will set up a phone call, virtual meeting or face-to-face meeting. Study contact will occur from our research staff, which includes study PI, the study staff (coordinators, etc.), and the patient's treatment team (e.g., oncologists, nurses, staff, etc.).

Subjects in the intervention arm will report to URMC labs at weeks four and eight after baseline for a lab draw to determine liver function (ALT, AST, and bilirubin) so that any hepatotoxicity can be monitored. Study personnel will call subjects to remind and coordinate the blood draws.

To track adherence, we will instruct subjects to bring all remaining study drug at their post-intervention assessment (T2) and the pills will be manually counted and pill counts will be entered onto the pill excel document.

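### The T2 DAFI cannot be computed as Table 4 defines it: the medication count is recorded at baseline only, and the chart chemistry has no date window

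*Combined protocol and SAP*

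**What the plan says.** Section 2.3 makes the DAFI one of two Aim 2 frailty measures, beside the Fried score. Section 5.5 calculates it in all subjects to describe "frailty status at the baseline assessment (T1) and at the post-intervention assessment (T2".

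Table 4 lists what the index needs. One line is "Number of regular medications taken daily". Four more are laboratory items: "Creatinine clearance", hemoglobin, albumin and a liver function test.

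Section 5.5 labels the medication paragraph "Medications (baseline only", and the data collection table in Section 5.3 has no medication row at T2. The Labs row of that table carries the tag "GA/A2/A3/EA1/EA3", so it feeds the geriatric assessment and Aim 2. It is filled by chart review at T1 and T2. The rule for choosing the chart value is: "Study personnel will obtain lab results from the CMP from electronic medical records with dates that are closest to assessment date". It sets no maximum age and provides for no draw if the chart holds nothing suitable.

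Two other rules bear on the same items. A complete blood count may come from a medical draw only "if the medical blood draw is conducted within the assessment week for T1 or T2"; otherwise the study draws one. For liver monitoring, Section 5.9 states: "Subjects in the intervention arm will report to URMC labs at weeks four and eight after baseline". In Section 5.7 usual care has a weekly call and no scheduled liver test.

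**The concern.** An index compared before and after treatment needs each item measured on the same terms at both visits. An item recorded once is either carried forward, and then cannot register change, or it is missing. A carried-forward item pulls the estimated DAFI effect toward zero and raises the pre-post correlation. Both matter here, because Section 11.1 intends the means, variances and pre-post correlations from this trial to feed the planning of the next one.

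A nearest-date rule without a limit can do the same to the chemistry: a survivor with no panel in the chart near T2 would contribute one value twice. The liver item raises a further question. Only one arm has tests scheduled between the visits, and Section 8.1 names hepatotoxicity as a risk of EGCG. An item sourced differently by arm could shift the comparison in either direction.

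**Working it through.** **1. The plan's own figure.** Sections 11.1 and 11.2 give 14 per arm, two-sided alpha 0.15, effect size 0.66, pre-post correlation 0.5 and 70% power. Under ANCOVA the residual SD is √(1 − 0.5²) = 0.866. The standardized effect is 0.66/0.866 = 0.762 and the noncentrality is 0.762 × √(14/2) = 2.02. The noncentral t with 25 df gives 70.4% (normal approximation 71.8%). The figure is reproduced. It concerns the Fried score; the plan gives no power, model or scoring rule for the DAFI.

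**2. Share of the index.** Table 4 as extracted has 50 items. The table text is broken, so the count is approximate. Under equal weights, *k* items carry *k*/50 of a 0–1 index.

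| Item(s) | Share | Status |
|---|---|---|
| Medication count | 1/50 = 0.02 | No T2 collection: certain |
| Creatinine clearance, albumin, liver test | 3/50 = 0.06 | No window: possible |
| Together | 4/50 = 0.08 | Upper limit |

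Hemoglobin is left out because the blood-count rule in Section 5.5 already supplies it within the assessment week, in both arms.

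**3. Reuse of one value.** T1 is week 0. T2 is week 13 and at the latest 12 + 3 = week 15 (Section 5.2). If the chart holds a single panel, that panel is the closest to both dates, and nothing in the rule excludes it. The documents do not say how many participants would lack a panel near T2.

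**4. The liver item by arm.** In the EGCG arm the week 8 result would be 13 − 8 = 5 to 15 − 8 = 7 weeks old at T2. Section 5.7 speaks of monthly monitoring while Section 5.9 names weeks four and eight, so a week 12 result is unclear; if it exists, its age would be 1 to 3 weeks. Those two passages must be reconciled. In usual care with no later clinical test, the last value would be:

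- 13 to 15 weeks old if the eligibility test fell at T1;
- 13 + 4 + 13 = 30 to 15 + 4 + 13 = 32 weeks old if it was done 3 months (13 weeks) before T0 (Section 3.3) and T1 followed T0 by 4 weeks (Section 5.2).

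This item is 0.02 of the index. If 5% to 20% of one arm were misclassified on it (an assumed range), the arm mean would shift by 0.05 × 0.02 = 0.001 to 0.20 × 0.02 = 0.004.

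**The case against.** **T2 mirrors T1.** Section 5.10 has the post-intervention visit follow the baseline format, so medications might be thought to be covered. This does not stand. The outcome list in Section 5.5 applies to both visits unless an entry says otherwise, and the medication entry does say otherwise.

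**The laboratory values are fresher in the EGCG arm.** A reader might infer this from the week 4 and week 8 draws. The documents do not support it as a general statement. Those draws cover ALT, AST and bilirubin only; creatinine and albumin are sourced identically in both arms. Even for the liver item it is only a possibility. It requires the results to sit in the chart used for the DAFI, and Section 10 says the draw is noted but that no other research information is entered. It also requires usual-care participants to have no recent clinical chemistry.

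**A post-randomization value becomes the baseline.** The nearest-date wording, taken alone, would allow it. But Section 5.5 opens by placing the baseline assessments before randomization, so such a value would conflict with the plan. Repeating the limit in the chemistry rule removes doubt.

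**More items are affected.** Hemoglobin has a windowed source. Walking appears in Table 4 but not among the six functions described for the ADL index. That is a labelling mismatch; the ADL form is completed at both visits in both arms, so the item is neither frozen nor unequally sourced.

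**The consequence is small.** This stands. The trial seeks preliminary data, the specified ANCOVA is for the Fried score, and Table 4 already contains items unlikely to move in 12 weeks, such as marital status and glaucoma.

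**Conclusion.** The plan contradicts itself on the DAFI. It requires a medication count at T2 and does not collect one. The chemistry rule also lets one chart value stand for both visits, and it leaves open a difference in source between arms for the liver item.

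At most about 4 of 50 items are involved, or 0.08 of the index, assuming equal weights and the extracted item count. Only 0.02 is certain. The 0.08 would be reached only if all three chemistry items were stale in every participant. It is a share of the index and not an estimate of bias.

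A reader might go further and infer that every T2 DAFI drops out under the complete-case rule in Section 11.2. The plan does not say that this rule works at item level, and it gives no rule for a missing DAFI item, so that inference is not established. The Fried score analysis, the sample size and the 70% power are unaffected.

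**What to change.** 1. Delete the baseline-only restriction in Section 5.5, record medications at T2 by the same chart review, and add the T2 entry to the Section 5.3 table.
2. In the chemistry rule, require the T1 value to be dated on or before randomization and the T2 value to fall in a stated window around T2. Allow no value to serve both visits, and apply the same rule in both arms. The width is the sponsor's choice: the assessment week used for the blood count is available, while a wider window would lose fewer values.
3. State that hemoglobin for the DAFI comes from the blood count obtained under the existing assessment-week rule.

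The cost is protocol wording, a second chart pull per participant and possibly some missing laboratory items. The plan should then say how the index is scored when an item is missing; several conventions are defensible. A fallback chemistry panel would reduce missing values, but it is an added procedure and is not needed to resolve the contradiction.

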#### **Exclusion Criteria: Study subjects must not:**

1. Have chemotherapy planned for the duration of the study.
2. Have abnormal liver function tests (ALT, AST, and bilirubin  $\geq 3$  times institutional upper limit of normal) per most recent available lab test (within 3 months of screening).
3. Have uncontrolled or unmanaged liver disease.
4. Consume more than 6 cups of green tea per day.
5. Have known allergies to caffeine.
6. Be diagnosed with a major psychiatric illness requiring hospitalization within the last year.
7. Be diagnosed with dementia.
8. Cannot provide informed consent due to lack of decision making capacity (as determined by the patient's oncologist) and has no patient-designated health care proxy per institutional policies and University of Rochester Cancer Control URCC guidelines.

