### Assessment of inflammatory markers

We will assess the blood concentrations of several immunological proteins (primary aim) and EGCG (only at the post-intervention time-point (T2)). All blood draws will occur in the Wilmot Cancer Center, UR-affiliated lab, or medical office if needed (in the latter case, we will use a trained study staff member to transport the samples to our storage facility). The location will be selected to minimize subject burden and if possible we will perform blood draws at the same time as regularly scheduled medical blood draw. Patients will report for the blood draw fasted for a minimum of 8 hours on the days of the scheduled blood draws. The blood will be drawn by trained staff and subjects will be informed to bring a breakfast/a snack to eat after the blood draw. The time of day will be noted, with future assessments at approximately the same time of day during post-testing.

A total of approximately 65-70 mL of blood (around 5 tablespoons) will be drawn at each time point (T1 and T2). All tubes will be collected by a study team member, processed, and then transferred to a secured -80°C freezer in lab space maintained by [name] in the Department of Surgery. We will collect the following:

1. Two red-top tubes for serum (10 mL each, 20 mL total). These tubes will be inverted 10 times, allowed to clot for 30 minutes at room temperature, centrifuged for 15 min at 1600 g and then frozen at -20°C or -80°C. These will be used to assess inflammation (cytokines, etc.) and EGCG concentration (only at the post-intervention time-point (T2)).
2. Two purple-top EDTA tubes for biological plasma levels (10 mL each, 20 mL total). One EDTA tube will be rocked 10 times, stored upright for a minimum of 30 min at room temperature and then spun. The other EDTA tube will be rocked 10 times and frozen at -20°C for 2-24 hours and then frozen at -80°C. These will be used to assess genetic biomarkers.
3. Two green-top tubes for peripheral blood mononuclear cells (10 mL each, 20 mL total). These will be pre-cooled and processed per SOP. This tube will be inverted 10 times and allowed to sit at room temp for 30 minutes, centrifuged for 15 min, and then frozen at -20°C or -80°C. These samples will be used to explore transcriptomic and epigenetic differences (using isolated PBMCs) between pre-frail and frail participants (Exploratory Aim 3)

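### No liver test is guaranteed in the EGCG arm after week 8: the only later planned value is a chart panel with no date limit and no backup draw

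*Combined protocol and SAP*

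**What the plan says.** **Scheduled liver draws.** Section 5.7 states that Arm 1 is checked monthly for ALT, AST and bilirubin, without naming weeks. Section 5.9 names them: "Subjects in the intervention arm will report to URMC labs at weeks four and eight after baseline for a lab draw". Section 5.11 pays Arm 1 subjects for T1, T2 and two liver draws.

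**The T2 liver value.** A liver item is planned at T2. Table 4 lists "Liver Function test" among the DAFI items, and section 5.5 uses the index for "frailty status at the baseline assessment (T1) and at the post-intervention assessment (T2"). The metabolic panel behind that item is abstracted from "electronic medical records with dates that are closest to assessment date for baseline assessment (T1) and post-intervention assessment (T2"). In section 5.3 the Labs row is completed by chart review, and its listed goals do not include Aim 1, the feasibility and safety aim.

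**How other laboratory values are handled.** A medical blood count is accepted only "if the medical blood draw is conducted within the assessment week for T1 or T2". Otherwise there is a fallback: "If there is no medical blood draw conducted within the appropriate assessment window for T1 or T2 then we will draw an additional" tube. The liver test used for eligibility in section 3.3 is also bounded: "per most recent available lab test (within 3 months of screening").

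**What depends on a liver value.** Under section 7, an unexplained rise of Grade 2 or more stops the drug for that subject, and one drug-related hepatotoxicity of Grade 3 or more in Arm 1 stops the study.

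**The concern.** Section 8.1 names hepatotoxicity as a risk of EGCG, and it is the only toxicity with its own study-stop rule. That rule works only if enzymes are measured. The weekly contacts in section 5.9 ask about symptoms, signs and illnesses, so they can pick up a case that makes itself felt but not a silent rise.

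A site could follow the plan exactly and have no liver result for a subject after day 56. A late silent rise would then miss three destinations: the Grade 3 study-stop rule, clinical follow-up of that subject, and the Aim 1 adverse event count that is to inform the next trial. Accrual is spread over 18 months, so a result obtained after one subject's last dose can still protect others who are being dosed or have yet to enrol.

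**Working it through.** **Inputs.** 84 daily pouches (5.8); liver draws at weeks 4 and 8 (5.9); T2 ideally in the first week after dosing and at most 3 weeks after it (5.2); payments (5.11); 20 subjects per arm and a 70% completion target (11.1); 65 to 70 mL drawn at T2 (5.5).

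**1. Dosing days.** 12 weeks × 7 = 84, which reproduces the pouch count in 5.8.

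**2. Number of scheduled liver draws.** Arm 1 payments: 2 × $20 + 2 × $10 = $60, the stated total. A third paid draw would give 2 × $20 + 3 × $10 = $70. The payments therefore agree with 5.9. They do not by themselves exclude an unpaid liver test at T2, so step 4 looks at the T2 tubes.

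**3. Exposure after the last scheduled draw.** Week 8 = day 56. 84 − 56 = 28 days; 28/84 = 33.3%.

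**4. Is there another source at T2?** The research tubes in 5.5 go to cytokines and EGCG concentration, genetic biomarkers, mononuclear cells and gene expression. None is assigned to liver enzymes. That leaves the chart panel:

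| Value | Date limit | Research draw if missing |
|---|---|---|
| Liver test for eligibility (3.3) | 3 months from screening | not stated |
| Blood count at T1 and T2 (5.5) | assessment week | yes, 5 mL |
| Metabolic panel at T1 and T2 (5.5) | none | none |

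The fallback for the blood count shows that the plan allows for subjects with no medical draw around T2. Subjects may be up to 10 years past treatment, so a routine panel at that time cannot be assumed.

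**5. Guaranteed liver tests after day 56.** None, for any of the 20 Arm 1 subjects.

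**6. Interval from week 8 to a test at T2.** On-time T2 falls on days 85 to 91: 85 − 56 = 29 and 91 − 56 = 35 days. Latest T2 is day 84 + 21 = 105: 105 − 56 = 49 days.

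**7. Reach and burden of a T2 test.** 0.70 × 20 = 14 subjects at the completion target, 20 if all attend. Extra blood: 5/70 = 7.1% to 5/65 = 7.7%.

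**The case against.** **The monthly wording may already cover it.** Monthly over 12 weeks could mean weeks 4, 8 and 12. But 5.9 is the specific schedule and stops at week 8, and the payment total fits two draws. The wording remains an inconsistency to repair, and the finding depends on reading 5.7 in the light of 5.9.

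**The blood count comparison is imperfect.** Circulating immune cells are Aim 3 outcomes, which alone would justify a tight window. The panel rule serves a frailty index and is not the safety plan. This is fair, and it is why the remedy belongs in 5.9 and 5.10. It does not supply a liver test after day 56.

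**Other protections exist.** There are two draws during dosing, weekly graded contacts reviewed with the oncologist and medical monitor, and committee oversight. Section 1.2 also cites a trial reporting 800 mg as safe and well tolerated. These lower the stakes but do not detect a silent late rise.

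**Stronger readings the documents do not support.**
- A reader might infer that the week 8 result would stand in as the T2 chart value. Section 5.5 abstracts a metabolic panel, 5.9 describes only three analytes, and section 10 limits what research information enters the medical record. Nothing shows that the week 8 result would qualify.
- A reader might equate no medical draw in the T2 week with no value near the end of dosing. A panel from day 83 would fall outside that week and still be informative.
- A reader might conclude that no liver value is planned at T2. One is, through the DAFI; it is simply not secured.

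**Conclusion.** The gap is real and worth closing. As written, no liver test is guaranteed after day 56, and 28 of 84 dosing days (33%) come after the last scheduled one. The conclusion rests on taking 5.9 and 5.11 as the operative schedule over the general statement in 5.7, and on the absence of any date limit or backup draw for the metabolic panel.

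The claim is that a silent late rise may go unmeasured, not that it will. The documents give no event rate, no onset timing and no frequency of routine panels in these survivors, so no probability of a missed case can be calculated.

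**What to change.** **Change.** In 5.9 and 5.10, require ALT, AST and bilirubin for every Arm 1 subject at the T2 blood draw. Accept a medical result only if it is dated after the last dose and within the T2 assessment week. Otherwise add one tube of about 5 mL and send it promptly to the clinical laboratory instead of freezing it with the research serum. Reword the monthly statement in 5.7 to match. The existing rules in section 7 then apply to the result, so no new stopping rule is needed.

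**Cost.** At most one small tube and a three-analyte assay for up to 20 subjects. No extra visit is needed, because blood "will be drawn at each time point (T1 and T2") already. If T2 measures are done by phone or Zoom, the planned blood draw must still take place.

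**Limits.** The result comes too late for the individual drug-stop rule. A transient rise may have resolved if T2 is late. Subjects who withdraw before T2 are not covered. Usual care has no safety liver draws, so the change adds to unequal ascertainment of liver events between arms; the adverse event table should say so.

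**Alternative.** A separate week 12 draw would hold the interval to 84 − 56 = 28 days, but it needs another visit, would bring Arm 1 payment to $70 at the current rate, and would still come too late to spare that subject meaningful exposure.
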